## Protocol Synopsis

Study Title:	The HepQuant SHUNT Test for Monitoring Liver Disease and Treatment Effects by Measuring Liver Function and Physiology		
Sponsor:	HepQuant LLC		
Device:	HepQuant SHUNT Liver Diagnostic Kit		
Funding BY:	HepQuant LLC		
Device Provided by:	HepQuant LLC		
Protocol:	ID:	HQ-US-SHUNT-1701	
	Version:	Original Version 5.0	
		Amended Version 6.0	
	Date:	Original date September 5, 2017	
		Amendment date May 15, 2018	
Compounds used in HepQuant SHUNT Test Kit:	[24-  C]cholic acid (13C-cholate or 13C-CA)		
	[2,2,4,4-  H(d4)]cholic acid (d4-cholate or d4-CA)		
Indication for Use:	Monitoring effects of Liver Disease and Treatment on Liver Function		
Gilead Parallel Clinical Trials:	GS-US-384-1943 (STELLAR 3) / Gilead Sciences:	IND 129570	
	GS-US-384-1944 (STELLAR 4) / Gilead Sciences;	IND 129570	
	GS-US-454-4378 (NASH F3/F4) / Gilead Sciences;	INDs pending	
Drug used in the Parallel Drug Trials:	Selonsertib, GS-0976, and GS-9674		
IDE Numbers (for use of the HepQuant SHUNT Test Kit in subjects co-enrolled in the Parallel Drug Trials):	G170034-S001 for GS-US-384-1943 (STELLAR 3)		
	G170034-S002 for GS-US-384-1944 (STELLAR 4)		
	IDE pending for GS-US-454-4378 (NASH F3 / F4)		
Study Centers/Pis:	This HepQuant SHUNT study is run in parallel to three Gilead clinical trials. Subjects are simultaneously participating in this HepQuant SHUNT study while participating in a Gilead-sponsored clinical trials for treatment of NASH. Because the HepQuant study will focus on the subjects with more advanced liver disease, the clinical sites participating in the HepQuant study must also be participating in one of the NASH F3 (STELLAR 3), NASH F4 (STELLAR 4), or GS-US-454-4378 (NASH F3 and F4) studies. The maximum number of clinical sites is 15 and the maximum number of study subjects is 100.		

Primary Objective:	To determine the utility of the Disease Severity Index (DSI) from the HepQuant SHUNT test for monitoring liver disease and treatment effects, DSI and the change in DSI ( $\Delta$ DSI) will be measured across all treatment arms.	
	The clinical significance of $\Delta$ DSI will be evaluated by analyzing the relationships of $\Delta$ DSI to changes in standard laboratory tests, clinical models, histologic stage of disease, and risk for clinical outcome.	
	We will also evaluate whether the HepQuant SHUNT test and DSI identify a treatment effect in the combined NASH F3 + NASH F4 cohorts, after unblinding of treatment assignments and completion of the primary analysis for Gilead's clinical trials. Treatment effect, as measured by DSI and $\Delta$ DSI, will be defined from the differences in DSI between treatment and placebo arms; and, compared to the treatment effect defined by changes in histology, standard laboratory tests, clinical models and by clinical outcomes.	
Secondary Objectives:	To determine the ability of baseline DSI, performed prior to treatment, to assess the severity of liver disease by: 1. correlation with other baseline tests of liver disease severity; and, 2. prediction of risk for future clinical outcome.	
Study Design:	Open Label HepQuant SHUNT Testing in All Subjects	
	STELLAR 3:	Baseline and Weeks 24, 48, and 240
	STELLAR 4:	Baseline and Weeks 24, 48, and 240
	GS-US-454-4378 (NASH F3 / F4):	Baseline and Weeks 24 and 48
Subjects, N:	Up to a total of 100 for all trials	
Clinical Sites, N:	Up to 15	
Target Populations:	NASH F3:	NASH Clinical Research Network (CRN) Fibrosis Stage 3
	NASH F4:	NASH CRN Fibrosis Stage 4 (compensated cirrhosis)
Compounds used in HepQuant SHUNT Test Kit:	[24-  C]cholic acid, 20 mg, intravenous injection	
	[2,2,4,4-  H(D)]cholic acid, 40 mg, oral solution	
Drug Treatment:	STELLAR 3:	Selonsertib vs Placebo
	STELLAR 4:	Selonsertib vs Placebo
	GS-US-454-4378 (NASH F3/F4):	Selonsertib, GS-0976, GS-9674 alone or in combination versus placebo.
Duration of Drug Treatment:	STELLAR 3:	240 weeks
	STELLAR 4:	240 weeks
	GS-US-454-4378 (NASH F3/F4):	48 weeks
Duration of Study and Drug Trial:	STELLAR 3:	252 weeks
	STELLAR 4:	252 weeks
	GS-US-454-4378 (NASH F3/F4):	52 weeks

Diagnostic and Eligibility Criteria:	Enrollment in the corresponding Gilead Trial, listed above
	Intravenous access for catheter placement
	Able to take orally administered solution
	No known allergy to any component of the HepQuant SHUNT test kit
Procedures and Frequency of the HepQuant SHUNT Testing:	
STELLAR 3:	Baseline and Weeks 24, 48, and 240
STELLAR 4:	Baseline and Weeks 24, 48, and 240
GS-US-454-4378 (NASH F3/F4):	Baseline and Weeks 24 and 48
Dose and Mode of Administration of Drug used in Drug Trial:	
STELLAR 3 and 4:	Selonsertib 6 or 18 mg orally daily
GS-US-454-4378:	Selonsertib 18 mg, GS-0976 20 mg, or GS-9674 30 mg for both monotherapy and combinations; Orally; Daily dosing
Reference Therapy in Drug Trial, Dose, Mode of Administration:	
	Placebo tablets; Orally; Daily
Criteria for Evaluation (HepQuant test parameters are the same for all studies):	
Baseline DSI:	DSI measured prior to randomization
ΔDSIi:	Change in DSI from baseline to time point, i
	Treatment Effect: ΔDSI i Treatment versus ΔDSI i Placebo
Primary Clinical Outcomes to link to baseline DSI and ΔDSIi:	
STELLAR 3:	Wk48: 1 Stage improvement in fibrosis without worsening NASH
	Wk48: Freedom from progression to cirrhosis
	Wk48: Freedom from decompensation, transplant, or death
	Wk240: 1 Stage improvement in fibrosis without worsening NASH
	Wk240: Freedom from progression to cirrhosis
	Wk240: Freedom from decompensation, transplant, or death
STELLAR 4:	Wk48: 1 Stage improvement in fibrosis without worsening NASH
	Wk48: Freedom from decompensation, transplant, or death
	Wk240: 1 Stage improvement in fibrosis without worsening of NASH
	Wk240: Freedom from decompensation, transplant, or death
GS-US-454-4378:	Endpoints as above for F3 and GJ F4 cases but only for 48 Weeks

**Statistical Methods:**

We will determine the utility of the Disease Severity Index (DSI) from the HepQuant SHUNT test to monitor liver disease and treatment effects by measuring liver function and physiology. We propose a three-step analytical process to achieve this goal. First, without knowledge of treatment arm, we will track DSI and the change in DSI,  $\Delta$ DSI, from baseline to on-treatment and follow-up timepoints. Second, we will apply separate survival models to evaluate  $\Delta$ DSI as a continuous variable and a 2 point or more change in DSI as dichotomous variable in the prediction of changes in other tests or models of liver disease severity and clinical outcomes. In HCV, an increase in DSI of 2 or more has been associated with disease progression; and, a decrease in DSI of 2 or more has been associated with improvement after viral clearance. Third, once the treatment arms have been unblinded we will evaluate if the use of the HepQuant SHUNT test and DSI identify a treatment effect in the combined cohort of NASH F3 plus NASH F4; and we will compare DSI to the primary measures of efficacy in each of the clinical trials. In terms of DSI, a treatment effect will be defined from the difference between the  $\Delta$ DSI of the treatment arm versus the  $\Delta$ DSI of the placebo arm. The significance of this difference will be evaluated using a two-sided t-test. Furthermore, we will link treatment effect defined by DSI to effects of treatment on other tests and clinical outcomes (bleeding from varices or portal hypertensive gastropathy, ascites, encephalopathy, SBP, progression to cirrhosis, and patient mortality or liver transplantation). We will use both generalized estimating equations (GEE) and profile analysis – profile of DSI between treatment and placebo groups at each time point – for additional primary endpoint analyses.

We will also determine the ability of baseline DSI, performed prior to treatment, to assess the severity of liver disease by: 1. correlation with other baseline tests of liver disease severity; and, 2. prediction of risk for future clinical outcome.

**Correlation of Baseline DSI with other baseline tests:**

STELLAR 3:	Liver histology; standard labs; MELD & CP scores
STELLAR 4:	Liver histology, standard labs, MELD & CP scores
GS-US-454-4378:	As above for F3 and F4 disease

In an analysis of the combined NASH F3 and F4 cohorts, we will correlate the baseline DSI with histology, lab tests, and clinical models by linear regression and Spearman’s correlation coefficients. Regression analysis will be used to obtain prediction and 95% CI of baseline B-K fibrosis score, standard lab tests, and clinical models based on DSI. In a secondary analysis of the combined NASH trials, we will use a discriminant analysis to compare the ability of baseline DSI to distinguish NASH F3 from NASH F4 to the ability of other tests and models to discriminate F3 from F4.

**Baseline DSI as Predictor of Risk for future clinical outcome:**

We will perform survival analysis for freedom from clinical outcome using Kaplan-Meier plots. Cox models will be used to estimate hazard ratios corresponding to 1 unit of DSI, controlling for other known risk factors of mortality (age, gender, smoking, etc). We will also apply separate survival models to evaluate DSI as a continuous variable and as above or below mean DSI as dichotomous variable in the prediction of clinical outcomes. In a secondary exploratory analysis of the combined NASH trials, we will use a discriminant analysis to compare the ability of baseline DSI to the ability of other tests and models to predict clinical outcomes.

Version 6.0  
May 15, 2018

## **HepQuant Contact Information**

## Glossary

$\beta$ -hCG  $\beta$ -human chorionic gonadotropin  
AE adverse event  
AH alcoholic hepatitis  
ALT alanine aminotransferase (also SGPT)  
ANC absolute neutrophil count  
APTT activated partial thromboplastin time  
AST aspartate aminotransferase (also SGOT)  
BID twice a day  
BLQ below the limit of quantitation  
BMI body mass index  
BW body weight  
CI Confidence Interval  
CLD chronic liver disease  
CP Child-Pugh (for clinical/laboratory classification of cirrhosis)  
CrCL creatinine clearance  
CT Computed Tomography  
CPK Creatine phosphokinase  
Cr serum creatinine  
CRF case report form(s)  
CYP Cytochrome P450  
dL Deciliter  
DNA deoxyribonucleic acid  
DSI Disease Severity Index (from HepQuant SHUNT test)  
DSPH Drug Safety and Public Health  
ECG Electrocardiogram  
eCRF Electronic case report form(s)  
EOT End of Treatment  
EU European Union  
FDA (United States) Food and Drug Administration  
GCP Good Clinical Practice (Guidelines)  
GGT gamma glutamyl transferase  
GI Gastrointestinal  
GT Genotype (viral)  
Hgb Hemoglobin  
HgbA1c Hemoglobin A1c  
HBsAg hemoglobin surface antigen  
HBV Hepatitis B virus  
HCC Hepatocellular carcinoma  
HCV Hepatitis C virus  
HFR Hepatic Filtration Rate  
IB Investigator Brochure  
ICH International Conference on Harmonisation  
IDE Investigational device exemption  
IEC independent ethics committee  
IMP Investigational Medicinal Product  
IND Investigational New Drug (Application)  
INR International Normalized Ratio of prothrombin time  
IRB institutional review board

IUD intrauterine device  
IU international units  
IV Intravenous  
IWRS interactive web response system  
Kg Kilogram  
L Liter  
LDL low-density lipoprotein  
LLN lower limit of the normal range  
LLOQ Lower limit of quantification  
LLT Lower-Level Term  
MCV mean corpuscular volume or mean cell volume  
MedDRA Medical Dictionary for Regulatory Activities  
mg Milligram  
mM Millimeter  
MH Mantel-Haenszel  
mL Milliliter  
min Minute  
mmHg millimeters mercury  
NAFLD Non-Alcoholic Fatty Liver Disease  
NASH Non-Alcoholic Steato-Hepatitis  
OTC Over the counter  
P-gp P-glycoprotein  
PG Pharmacogenomic  
PH portal hypertension  
PI Protease inhibitor  
PO by mouth  
QD once daily (use only in tablets)  
PK Pharmacokinetic  
PSC Primary sclerosing cholangitis  
PT prothrombin time  
RBC red blood cell count  
RBV Ribavirin  
RNA ribonucleic acid  
RVR rapid virologic response  
SAE serious adverse event  
SD Standard deviation  
SEL selonsertib  
SMV Olysio/Simeprevir  
SOC Standard of Care  
SOF Sovaldi/Sofosbuvir  
SOP Standard operating procedure  
SUSAR Suspected Unexpected Serious Adverse Reaction  
SVR Sustained Virologic Response  
SVR 4 Sustained viral response 4 weeks after discontinuation of study treatment  
SVR 12 Sustained viral response 12 weeks after discontinuation of study treatment  
SVR 24 Sustained viral response 24 weeks after discontinuation of study treatment  
TVR Telaprevir  
US United States  
WBC white blood cell count

## **1.0 Introduction**

### **1.1 Parallel Study Design**

#### **1.1.1 Use of the HepQuant SHUNT Test in Clinical Trials**

The HepQuant SHUNT test, which is provided as a HepQuant SHUNT Liver Diagnostic Kit, is a minimally-invasive test of liver function and physiology which has been designated by the FDA as an investigational drug/device combination product. Because the HepQuant SHUNT test is an investigational product, its use in clinical trials requires an investigational device exemption (IDE) issued from FDA. HepQuant has already secured IDEs for performing the HepQuant SHUNT test in subjects enrolled in Gilead's clinical trials. HepQuant's IDE numbers for the Gilead trials are:

- G170034-S001 for the GS-US-384-1943 trial of non-alcoholic steatohepatitis (NASH) fibrosis stage 3 (STELLAR-3),
- G170034-S002 for the GS-US-384-1944 trial of NASH and compensated cirrhosis (STELLAR-4), and
- IDE pending for the GS-US-454-4378 trial of NASH fibrosis stage 3 and NASH fibrosis stage 4.

#### **1.1.2 The HepQuant study as a Parallel Study**

In this HepQuant study the HepQuant SHUNT test will be performed in subjects enrolled in the three Gilead trials noted above. The HepQuant study protocol, informed consent, and documents govern the administration, monitoring, and analyses of the HepQuant SHUNT test.

The HepQuant study is to run parallel to the Gilead clinical trials. The time points for the HepQuant SHUNT tests coincide with pre-specified time points within the Gilead clinical trials. Subjects enrolled in GILEAD's STELLAR and GS-US-454-4378 (NASH F3/F4) trials may participate concurrently in this HepQuant sponsored investigational device study at participating US sites only once approved by the applicable IRB/IEC.

### **1.1.3 Coordination and Sponsorship**

The main eligibility criteria for enrollment into the HepQuant study is enrollment into one of the three Gilead clinical trials listed above in Section 1.1.1 and criteria noted in Section 5.2. A participant in the HepQuant study will consent to one of the Gilead clinical trials and the HepQuant study at the same visit or when the subject qualifies for one of the above listed Gilead studies. Enrollment into one of the Gilead clinical trials is required for enrollment into the HepQuant study.

The HepQuant study covers all procedures, oversight, and monitoring related to the HepQuant SHUNT test. HepQuant LLC is the sole Sponsor of the HepQuant study. Gilead has contracted with HepQuant for the results of all the HepQuant tests performed in the subjects enrolled in the Gilead trials.

All other aspects of Gilead's clinical trials are covered under Gilead's main protocols and contracts with clinical sites. Gilead Sciences is the sponsor of the three clinical trials noted above. HepQuant test results will be sent to Gilead and Gilead will conduct all correlation analyses with other parameters being collected in the Gilead protocols. HepQuant will request the results of these analyses from Gilead.

### **1.1.4 Co-enrollment**

Subjects enrolled in this HepQuant study of the diagnostic utility of the HepQuant SHUNT test are co-enrolled in a Gilead clinical trial of treatment with selonsertib. Justification for co-enrollment includes:

- Complementary, not competing, interests and endpoints for the two studies
- Collaboration agreement between HepQuant and Gilead
- Independent informed consents
- Gilead will conduct correlation analysis of study results

Co-enrollment into the two studies does not violate any of the ethical principles of respect for persons, beneficence, and justice that guide research involving human subjects.

## 1.2 Rationale for Conducting this Study

Why conduct this research study? There is an unmet medical need for a non-invasive or minimally-invasive test that accurately measures liver function and physiology. The HepQuant SHUNT Test is minimally-invasive and measures hepatocyte function and inflow to the liver from the simultaneous clearances (hepatic filtration rates, HFRs) of cholate from systemic and portal circulations. The Test quantifies portal-systemic shunting (SHUNT) and generates a liver disease severity index (DSI) [1]. DSI is a score from 0 (no disease) to 50 (terminal illness) that is a composite of both HFRs and correlates with stage of fibrosis, presence of varices, especially large varices, and risk for future clinical outcomes [2-8]. DSI is the primary output variable from the HepQuant SHUNT test. The HepQuant SHUNT test potentially satisfies the unmet medical need for a minimally-invasive test of global liver function and physiology.

HepQuant believes that DSI from baseline and serial HepQuant SHUNT tests will be useful in defining baseline disease severity and that the change in DSI,  $\Delta$ DSI, will detect clinically meaningful changes in liver disease and responses to treatment.

## 1.3 The Gilead Clinical Trials

As stated above, HepQuant believes that baseline DSI and change in DSI,  $\Delta$ DSI, are useful for monitoring liver disease and treatment effects. HepQuant proposes collaborative parallel studies with pharmaceutical drug trials to validate DSI and  $\Delta$ DSI for monitoring.

The Gilead trials are double-blind, randomized, placebo-controlled clinical trials – the HepQuant study will be run in parallel and coordinated with three Gilead trials:

1. GS-US-384-1943 (STELLAR-3); subjects with non-alcoholic steatohepatitis (NASH) and bridging (F3) fibrosis
2. GS-US-384-1944 (STELLAR-4); subjects with NASH and compensated cirrhosis (F4)
3. GS-US-454-4378; subjects with NASH and bridging (F3) fibrosis or compensated cirrhosis (F4)

The Gilead IND for selonsertib is 129570. The INDs for GS-0976 and GS-9674 are pending. This is provided to HepQuant for cross-referencing. HepQuant's letters of FDA's issuance of the IDEs for each of the trials are provided in Appendix A.

## 2.0 Primary and Secondary Objectives

As described in Section 1.2, the Disease Severity Index (DSI) from the HepQuant SHUNT test is a score from 0 to 50 based upon the dual simultaneous clearance of cholates (CAs) from systemic (13C-CA) and portal circulations (4D-CA). DSI is the primary output from the HepQuant SHUNT test; and, both DSI and change in DSI ( $\Delta$ DSI) may be useful in monitoring liver disease and treatment effects.

### 2.1 Primary Objective

The primary objective is to determine the utility of the Disease Severity Index (DSI) derived from the HepQuant SHUNT test, which measures liver function and physiology, for monitoring liver disease and treatment effects.

- Utility will be defined by measuring DSI and the change in DSI ( $\Delta$ DSI) across all treatment arms. DSI and  $\Delta$ DSI will be evaluated in real time.
- The clinical significance of changes in DSI will be evaluated by analyzing the relationship of  $\Delta$ DSI to changes in histologic stage of disease, standard laboratory tests, clinical models, or risk for clinical outcome. Some of the proposed comparative analyses will only be performed after unblinding of treatment arms and completion of analyses for the main Gilead trials and may be conducted by Gilead.
- Treatment effects will only be determined after unblinding the treatment arms and completion of the analyses for the main Gilead trials. In terms of DSI, treatment effects will be determined from the differences in DSI and  $\Delta$ DSI between treatment and placebo arms. The analyses will be conducted by Gilead.

**Clinically-meaningful outcomes.** As noted above, the subjects will be followed for clinical outcomes in the Gilead trials. In the case of STELLAR 3 and 4, the follow-up for clinical outcomes (bleeding from varices or portal hypertensive gastropathy, ascites, encephalopathy, liver-related death) will be up to 240 Wks – the  $\Delta$ DSI associated with development of clinical outcome at both Wk48 and Wk240 will be analyzed. In the case of GS-US-454-4378, the follow-up for clinical outcomes will be for 48 Weeks.

**Unblinding Treatment Arms.** Each of the Gilead NASH trials is placebo-controlled. Once the allocation code for the Gilead clinical trial is unblinded, HepQuant will request the treatment allocation from Gilead in order to analyze the HepQuant SHUNT results in the context of treatment versus placebo. The  $\Delta$ DSI of the treatment arm will be compared to the  $\Delta$ DSI of the placebo arm. We anticipate that the  $\Delta$ DSI in the placebo arm will either not change reflecting stability, or be positive, reflecting the natural progression of liver disease. If treatment is effective the  $\Delta$ DSI of the treatment arm should be negative – implying a lowering of disease severity and improvement in liver function and physiology. A treatment effect based on DSI will be determined from comparison of  $\Delta$ DSI of the treatment and control arms.

## 2.2 Secondary Objective

The secondary objective is to determine the ability of baseline DSI, performed prior to treatment, to assess the severity of liver disease by:

- correlation with other baseline tests of liver disease severity; and,
- prediction of risk for future clinical outcome.

**Tests of liver disease severity to compare to baseline DSI.** Standard tests for assessing the severity of liver disease include liver histology (stage of fibrosis), standard blood tests (elevated bilirubin and INR, and reduced albumin and platelet count), and clinical models (MELD and CTP scores). Subjects enrolled in the Gilead trials will undergo a battery of these tests, at baseline. Through requests to Gilead for specific data analyses, HepQuant's baseline DSI will be compared to the baseline results of these other measurements, such as fibrosis score on liver biopsy, clinical laboratory tests and models, and other exploratory tests of stage of fibrosis (elastography [FibroScan, MRE] and biomarkers).

**Clinically-meaningful outcomes.** The subjects will be followed for clinical outcomes. In the case of F3/F4 NASH, the rates of development of clinical outcomes (progression to cirrhosis, bleeding from varices or portal hypertensive gastropathy, ascites, encephalopathy, liver-related death) will be relatively slow so the follow-up is up to 240 weeks – the baseline DSI associated with development of clinical outcome at both Wk48 and Wk240 will be analyzed.

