### **3.3.4 Measuring Disease Severity in NAFLD and NASH**

Disease severity in NAFLD and NASH is based upon clinical, laboratory, and histologic criteria. Clinical and laboratory criteria are useful in defining disease severity only in the

late stages of disease. Histologic criteria define the spectrum from minimal change, through stages of advancing fibrosis and inflammation to cirrhosis [58,59].

In multi-variable analyses of clinical, laboratory, and histologic features, hepatic fibrosis (NASH CRN fibrosis stage >2) is the only factor that consistently predicts risk for liver-related mortality in NASH [57-65]. MELD (model for end-stage liver disease) and CTP (Child-Turcotte-Pugh) clinical models can define which cirrhotic NASH patients are at highest risk for death [65].

A non- or minimally-invasive method for measuring disease severity in NAFLD and NASH is desirable. The HepQuant SHUNT test to be used in this study provides a disease severity index (DSI) which correlates with other measures of disease severity. DSI can define baseline hepatic impairment and serial DSI measurements can track changes in response to treatments.

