### **8.3.3 Baseline DSI as a predictor of Clinical Outcome**

Our goal is to correlate the baseline DSI with risk for clinical outcomes. The primary clinical outcomes in the Gilead clinical trials include:

- STELLAR 3: Wk48: Decrease fibrosis stage  $\geq 1$ ; no worsening NASH  
Wk48: Freedom from progression to cirrhosis  
Wk48: Freedom from decompensation, transplant, death  
Wk240: Decrease fibrosis stage  $\geq 1$ ; no worsening NASH  
Wk240: Freedom from progression to cirrhosis  
Wk240: Freedom from decompensation, transplant, death
- STELLAR 4: Wk48: Decrease fibrosis stage  $\geq 1$ ; no worsening NASH  
Wk48: Freedom from decompensation, transplant, death  
Wk240: Decrease fibrosis stage  $\geq 1$ ; no worsening NASH  
Wk240: Freedom from decompensation, transplant, death
- GS-US-454-4378 (F3): Wk48: Decrease fibrosis stage  $\geq 1$ ; no worsening NASH  
Wk48: Freedom from progression to cirrhosis  
Wk48: Freedom from decompensation, transplant, death
- GS-US-454-4378 (F4): Wk48: Decrease fibrosis stage  $\geq 1$ ; no worsening NASH  
Wk48: Freedom from decompensation, transplant, death

We will perform survival analysis for freedom from clinical outcome by Kaplan-Meier plots. Cox models will be used to estimate hazard ratios corresponding to 1 unit of DSI, controlling for other known risk factors of mortality (age, gender, smoking, etc). We will also apply separate survival models to evaluate DSI as a continuous variable and as above or below mean DSI as dichotomous variable in the prediction of clinical outcomes. In a secondary analysis of the combined NASH trials, we will use a discriminant analysis to compare the ability of baseline DSI to the ability of other tests and models to predict clinical outcomes.

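### Does naming progression to cirrhosis for F3 and F4 together, with the survival event and fibrosis stage left unstated, undermine the baseline-DSI outcome analysis?

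*Combined protocol and SAP*

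**What the plan says.** The second half of the secondary objective is that baseline DSI predicts later clinical outcome.

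- **Section 2.2** describes the outcomes for both stages in one sentence, beginning "In the case of F3/F4 NASH, the rates of development of clinical outcomes (progression to cirrhosis, bleeding from varices". The list goes on to ascites, encephalopathy and liver-related death. It adds that the "baseline DSI associated with development of clinical outcome at both Wk48 and Wk240 will be analyzed".
- **Section 8.3.3** lists outcomes by trial, stage and visit. "Wk240: Freedom from progression to cirrhosis" stands under STELLAR 3 only, and its Week 48 counterpart under STELLAR 3 and the F3 part of GS-US-454-4378. "Freedom from decompensation, transplant, death" stands under every trial and both stages. Fibrosis improvement without worsening of NASH is also listed throughout.
- **Section 8.3.3, methods:** "We will perform survival analysis for freedom from clinical outcome by Kaplan-Meier plots", and "Cox models will be used to estimate hazard ratios corresponding to 1 unit of DSI, controlling for other known risk factors of mortality", with age, gender and smoking as open-ended examples. Combining the NASH trials is mentioned there only for the discriminant analysis. The Synopsis has nearly the same text.
- **Section 3.3.4** says that "hepatic fibrosis (NASH CRN fibrosis stage >2) is the only factor that consistently predicts risk for liver-related mortality in NASH".
- **Section 2.1** limits follow-up in the third trial: "In the case of GS-US-454-4378, the follow-up for clinical outcomes will be for 48 Weeks".
- **Section 8.2.3** reports that STELLAR 3 and STELLAR 4 contributed 5 and 4 subjects.

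**The concern.** F4 subjects enter with compensated cirrhosis (Synopsis, Target Populations; Section 5.1), so they cannot progress to it. If the Section 2.2 list were used as one event in pooled F3 and F4 subjects, F4 subjects would sit in the risk set for an event they cannot have. Section 1.2 says that DSI correlates with fibrosis stage, so F4 subjects would also tend to have the higher DSI. That combination pulls the DSI hazard ratio down and could make a useful marker look useless.

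Section 8.3.3 does not expressly exclude this reading. It names neither the event nor the cohort for the Kaplan-Meier and Cox models, and it does not mention stage among the covariates. The two lists also differ on death: Section 2.2 has liver-related death and no transplant, while Section 8.3.3 has transplant and death without qualification. Section 2.2 further speaks of Week 240 for F3/F4 NASH in general, although most subjects would come from a trial that ends follow-up at Week 48. Half of the secondary objective would be affected.

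**Working it through.** **1. Which list governs.** The documents state no event count, hazard ratio or power for this analysis, so there is no figure to reproduce. Setting the sections side by side:

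| Point | Section 2.2 | Synopsis, 8.2.2, 8.3.3 |
|---|---|---|
| Progression to cirrhosis | F3/F4 in one sentence | F3 only |
| Week 240 | F3/F4, as a maximum | STELLAR 3 and 4 only |
| Death, transplant | liver-related death; no transplant | death; transplant |

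Section 2.2 explains why follow-up is long. The analysis section lists outcomes by stage and visit. Two of its listed items are worded as freedom from an event, and the survival analysis is for freedom from clinical outcome. The natural reading is one model for each of those two items, in the cohorts where it is listed. No section counts F4 subjects as progressing.

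**2. The feared analysis, under assumed inputs.** None of these inputs is in the documents: equal F3 and F4 numbers, within-stage DSI SD 4, true within-stage hazard ratio 1.10 per point, 48-week decompensation risk 1% in F3 and 4, 8 or 15% in F4, F3 cirrhosis at the Week 48 biopsy 5, 10 or 20%, and an F4-minus-F3 mean DSI gap of 3, 5 or 8. That makes 27 settings. Results for a pooled composite without stage:

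- below 1: 4 settings, lowest 0.96 (gap 8, F4 risk 4%, cirrhosis 20%);
- 1.00–1.09: 16 settings;
- within 0.01 of 1.10: 4 settings;
- above 1.11: 3 settings, highest 1.13.

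With no gap the result is 1.09–1.10, so there is no bias. Changing one assumed input at a time changes the picture:

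- SD 8: range 1.03–1.11, none below 1;
- true hazard ratio 1.20: 1 of 27 below 1;
- true hazard ratio 1.05: 8 of 27 below 1.

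**3. The outcome that F3 and F4 share.** For decompensation, transplant or death alone, under the same base inputs, the unstratified hazard ratio is 1.13–1.19 and the stage-stratified one 1.09–1.11. The first measures overall prognostic value and the second value within stage. Both are legitimate.

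**4. Events at the 100-subject cap, 50:50.** Expected events = 50 × 0.01 + 50 × F4 risk:

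- F4 risk 4%: 0.5 + 2.0 = 2.5
- F4 risk 8%: 0.5 + 4.0 = 4.5
- F4 risk 15%: 0.5 + 7.5 = 8.0

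Approximate SE of the log hazard ratio = 1/(√events × SD), with SD 4:

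- 2.5 events: 1/(1.581 × 4) = 0.158; interval 1.10 × exp(±1.96 × 0.158) = 0.81–1.50
- 8.0 events: 1/(2.828 × 4) = 0.088; interval 0.93–1.31

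Each interval contains both ranges in step 3.

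**5. What stratifying would add.** Expected F3 events are 0.5, and the chance of none is 0.99^50 = 61%. With none, F3 contributes nothing to a stratified model and the estimate comes from F4 alone. The stage coefficient of an adjusted model would not be estimable.

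**6. Week 240.** At most 5 + 4 = 9 subjects can reach it, 5 of them F3. With no events, the exact 95% upper limit is 1 − 0.025^(1/9) = 34%, or 1 − 0.025^(1/5) = 52% for the 5 F3 subjects. These data can only be described, whatever the model text says.

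**The case for a change.** The best case for a change is that the plan commits to Cox models and names no event, cohort or handling of stage, so two analysts could follow it differently. Section 1.1.3 gives the correlation analyses to the drug-trial sponsor, which is a reason to write the choices down beforehand. The cost would be a few lines.

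Part of this stands. The event is not named model by model, the two lists do differ on death and transplant, and stage is not mentioned. Nor could the bias in a pooled composite be dismissed as noise. The worst setting would have 2.5 + 50 × 0.20 = 12.5 events. The approximate interval around 1.10 is then 0.96–1.26, so the distorted value of 0.96 would sit at its lower edge.

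But that composite has to be put together from Section 2.2 against the stage-specific lists; the plan does not state it. Fibrosis stage is left open, not excluded: the covariates are known mortality risk factors given by example, and Section 3.3.4 names fibrosis as one. Its cut above stage 2 covers both F3 and F4, so it supports fibrosis as a risk factor without showing an F3-versus-F4 difference. On death and transplant, Section 8.3.3 restates the drug trials' own primary outcomes, so an analyst using those data would take that definition. Finally, Section 8.3.3 says in the first person that the survival analysis will be done, so it is not established that another party makes these choices. The research agreement mentioned in Section 5.3.3 is not part of the documents and settles nothing either way.

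**Conclusion.** No change to the plan follows. The joint wording in Section 2.2 is a clerical looseness that the stage-specific lists in the Synopsis, 8.2.2 and 8.3.3 already put right, and the Week 240 wording gives a maximum that those lists assign to STELLAR only. The unnamed event, cohort and covariates are detail that a competent analyst would fill sensibly: progression to cirrhosis in F3, decompensation, transplant or death where listed, and stage considered among the risk factors.

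No bias is shown in an analysis that the plan states. The hazard ratios of 0.96–1.13 belong to a composite that it does not state and depend on the assumed SD, hazard ratio, DSI gap and event rates. For the shared outcome, the unstratified estimate is valid as overall prognostic value. With about 2.5 to 8 expected events, about 0.5 of them in F3, a stratified estimate beside it would be close to F4-only and would not alter a conclusion. The event counts rest on the 100-subject cap, an equal split and assumed 48-week risks of 1% in F3 and 4–15% in F4. The Week 240 limit of 9 subjects comes from the documents.
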